2. A diagnosis or suspicion of immunodeficiency disorder either in the infant or in an immediate family member.
3. A diagnosis or suspicion of bleeding disorder that would contraindicate administration of bOPV or nOPV2 or collection of blood by venipuncture.
4. Acute diarrhoea, infection or illness at the time of enrolment (6 weeks of age) that would require infant's admission to a hospital.
5. Acute vomiting and intolerance to liquids within 24 hours before the enrolment visit (6 weeks of age).
6. Evidence of a chronic medical condition identified by a study medical officer during physical exam.
7. Receipt of any polio vaccine (OPV or IPV) before enrolment based upon documentation or parental recall.
8. Known allergy/sensitivity or reaction to polio vaccine, or its contents.
9. Infants from multiple births. Infants from multiple births will be excluded because the infant(s) who is/are not enrolled would likely receive OPV through routine immunization and transmit vaccine poliovirus to the enrolled infant. Even if all births from a multiple birth could be enrolled in the study, we will exclude multiple births as discontinuation of one may lead to discontinuation of multiple vaccine recipients.
10. Infants from premature births (<37 weeks of gestation).

Sibling

1. Participant in a previous poliovirus vaccine clinical trial.
2. Unable to participate in the study until and including the Clinic Visit at 10 weeks (age of vaccine recipient).
3. A diagnosis or suspicion of immunodeficiency disorder either in the sibling or in an immediate family member.
4. Acute diarrhoea, infection or illness at the time of enrolment that would require sibling's admission to a hospital.
5. Evidence of a chronic medical condition identified by a study medical officer during physical exam.

Discontinuation Criteria

Vaccine Recipient

1. Withdrawal of consent for participation for any reason.
2. Request by parents of vaccine recipient to terminate all study procedures.
3. Identification of immunodeficiency disorder, bleeding disorder or another medical condition for which continued participation, in the opinion of the principal investigator, would pose a risk to the vaccine recipient to continue in the study.
4. Receipt of immunosuppressive medications.

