5. Receipt of any polio (OPV or IPV) vaccine outside of study after enrolment (as per parent's report). Vaccine recipients who received polio vaccines outside of the study, including any polio vaccine administered in polio campaigns, would be excluded from further study procedures.
6. Temporary discontinuation may occur when there has been a temporary suspension of study activities. Study enrolment will be suspended from 12 weeks before the start of polio campaigns in the study areas to 6 weeks after the completion of polio campaigns in the study areas. This measure is to prevent potential interference from polio vaccine administered during polio campaigns in the study areas. If vaccine recipients receive vaccine during polio campaigns, they would be discontinued from further study procedures.

7. Unable to collect or obtain blood at enrolment (Clinic Visit at 6 Weeks of Age).
8. Allergic reaction to a prior dose of polio vaccine, or its contents.
9. Premature termination of the study.

Sibling

1. Vaccine recipient is discontinued from the study.
2. Withdrawal of consent for participation for any reason.
3. Receipt of any polio (OPV or IPV) vaccine after enrolment (as per parent's report). Siblings who receive polio vaccines during their participation in the study, including any polio vaccine administered in polio campaigns, would be excluded from further study procedures.

Description of Study Vaccines

Two polio vaccines will be used in the study: bOPV and nOPV2

1. Bivalent oral polio vaccine (bOPV)

- a. Manufacturer: Bio Farma
- b. Presentation: the vaccine will be available in multi-dose vials
- c. Formulation: Each dose (2 drops = 0.1 ml).
- d. Administration: one vaccine vial will be used per participant.
- e. Previous use at icddr,b: bOPV is part of the routine immunization schedule in Bangladesh.

2. Candidate 1 novel monovalent oral poliovirus vaccine type 2 (nOPV2)

- a. Manufacturer: Bio Farma

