Concomitant Medications and Vaccines

There will be no restrictions on the use of medications or treatments for concomitant diseases. If the vaccine recipient needs to receive medications that cause immunosuppression, the vaccine recipient will be discontinued from the study.

If the vaccine recipient receives a dose of either polio vaccines (OPV or IPV) outside of the study during the study period, the vaccine recipient will be discontinued from the study. Parents will be encouraged and offered an opportunity to have their child vaccinated with routine childhood immunizations during study clinic visits, in accordance with Bangladesh EPI's vaccination schedule. Other non-routine immunizations will not be prohibited if they do not contain polio vaccines.

Specimen Collection, Handling and Testing

Sera: Table 2 summarizes the blood samples that will be collected for serological testing. All study visits requiring blood collection will collect 1 ml of blood. Blood will be stored temporarily in the study clinic and transported from the clinic to the icddr,b virology laboratory at 2–8 degrees Celsius within 6 to 8 hours of collection. Then sera will be separated by centrifugation in icddr,b virology lab within one hour. Tubes with haemolysed blood will be discarded following standard biohazard waste disposal protocol. After sera have been aliquoted separately for testing of poliovirus (0.2 mL), the remaining sera will be stored at icddr,b in cryovials with CDC provided labels that include vaccine recipient identification number (PID) and study protocol number. At all visits, only one aliquot (0.2 mL) will be prepared for shipment for Atlanta. The samples stored at icddr,b are reserve samples that may need to be shipped to CDC in the event that samples in the initial shipment were adversely affected, resulting in

the inability to perform testing or uninterpretable results. Cryovial tubes that will be sent to CDC for testing will be stored in a -20 degree Celsius freezer. The rest of the aliquoted sera will be stored at -70 degree Celsius at icddr,b.

Table 2. Summary of sera samples for serological testing

Age of vaccine recipient	Blood collected from arms	Volume of blood collection	Sera available	Sera for poliovirus testing	Sera stored at icddr,b
6 weeks	All arms	1 ml	0.4 ml	0.2 ml	0.2 ml
10 weeks	All arms	1 ml	0.4 ml	0.2 ml	0.2 ml
14 weeks	All arms	1 ml	0.4 ml	0.2 ml	0.2 ml
18 weeks	All arms	1 ml	0.4 ml	0.2 ml	0.2 ml

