This is an open-label, non-inferiority, randomized clinical trial that will compare immune response to types 1, 2 and 3 polioviruses of nOPV2 and bOPV when co-administered compared to nOPV2 and bOPV given alone. The study will recruit 795 vaccine recipients in three arms. Vaccine recipients will be enrolled at 6 weeks of age and followed until 18 weeks of age, for 12 weeks of follow-up. For each vaccine recipient enrolled, one sibling will be enrolled at the same time and followed for 4 weeks .

General Analytical Issues

The data will be analysed by study investigators that include epidemiologists and statisticians. Statistical packages that will be used for the analysis include R, SAS and STATA.

For assessing immunity to polio, seropositivity is defined as reciprocal polio neutralizing antibody titers

of at least 1:8. Immune response will be defined as either seronegative vaccine recipients ($<1:8$ titers) who become seropositive ($\geq 1:8$) [seroconversion] or vaccine recipients who demonstrate a four-fold

increase in titer (boosting). Baseline maternal antibody titers will be determined at 6 weeks of age and the estimated maternal antibody level at each blood collection will be calculated assuming an exponential decline with a half-life of 28 days.

For assessing fecal viral shedding, detection of nOPV2 or bOPV vaccine virus in stool specimens from vaccine recipient or sibling at either 1, 2, or 4 weeks post-vaccination of the vaccine recipient at 6 weeks of age will be defined as positive for viral shedding. For assessing the detection of household transmission, presence of transmission will be defined as the sibling of the vaccine recipient testing positive for nOPV2 vaccine virus at either 1, 2, or 4 weeks post-vaccination of the vaccine recipient at 6 weeks of age.

To characterize the intertypic recombinants in a subset of stool specimens of vaccine recipients and siblings after one dose of nOPV2 given with or without bOPV, amplicon sequences from long-read sequencing methods will be used to confirm genome structure. Amplicon sequences will also be mapped against all three Sabin vaccine reference sequences to generate coverage plots.

Primary Analytical Approach

The primary analytical approach will be intention-to-treat. To evaluate the primary objectives, the intention-to-treat analysis will be restricted to vaccine recipients who:

- Have not withdrawn consent for receipt of vaccines and follow-up evaluations since enrolment.

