- Vaccine recipient received the scheduled study vaccination at 6 weeks of age.

Table 5: Study arms comparison, study endpoints, and results by objective

Study Objective	Study Arms Comparison	Endpoint (vaccine recipient age)	Results Included in Analysis
Primary			
1. To compare type 2 immunogenicity of two doses of nOPV2 with two doses of nOPV2 co-administered with bOPV.	A vs. B	14 weeks	Serology: 6, 10, 14 weeks
2. To compare type 1 and 3 immunogenicity of two doses of bOPV with two doses of bOPV co-administered with nOPV2.	C vs. B	14 weeks	Serology: 6, 10, 14 weeks
Secondary			
1. To compare type 2 immunogenicity of one or three doses of nOPV2 with the same number of doses of nOPV2 co-administered with bOPV.	A vs. B	10 weeks	Serology: 6, 10 weeks
		18 weeks	Serology: 6, 10, 14, 18 weeks
2. To compare type 1 and 3 immunogenicity of one or three doses of bOPV with the same number of doses of bOPV co-administered with nOPV2.	C vs. B	10 weeks	Serology: 6, 10 weeks
		18 weeks	Serology: 6, 10, 14, 18 weeks
3. To assess the presence of fecal viral shedding (as determined by real-time RT-PCR) over time following one dose of nOPV2, bOPV, or co-administered nOPV2 and bOPV.	Descriptive with comparisons of A vs. B and B vs. C	10 weeks (i.e. 4 weeks post-vaccination)	Stool: 7 (Arm A only), 8, 10 weeks from vaccine recipient
4. To estimate household transmission of nOPV2 by assessing the presence of fecal viral shedding (as determined by real-time RT-PCR) among siblings of vaccine recipients.	Descriptive	10 weeks (i.e. 4 weeks post-vaccination)	Stool: 7 (Arm A only), 8, 10 weeks from sibling
5. To assess the occurrence and genomic characteristics of intertypic recombinants in stool specimens of vaccine recipients and siblings after one dose of nOPV2 given with or without bOPV.	Descriptive with comparison of A vs. B	10 weeks (i.e. 4 weeks post-vaccination)	Stool: 8, 10 weeks from vaccine recipient and sibling

Adverse Events (AEs)

Safety will be assessed by:

- Incidence rate of solicited systemic AEs 24–48 hours after the first study vaccination.
- Incidence rate of unsolicited AEs during entire study period.
- Incidence rate of serious AEs during entire study period.

Data Safety Monitoring Plan (DSMP)

Records to be kept

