Outcome (circle what applies): Ongoing / Resolved without sequela / Resolved with sequela / DeathDate when event resolved or death (dd/mm/yy): / /

Did this AE lead to discontinuation from the study or from future vaccinations? Yes / No

Adverse Event Form (cont.)**Study group allocation:** Specify which study group the child was allocated (*circle the answer*):

A: nOPV2 @ 6, 10, and 14 weeks
 B: nOPV2 + bOPV @ 6, 10, and 14 weeks
 C: bOPV @ 6, 10, and 14 weeks

Study vaccines administered:

Clinic visit	Study vaccines administered	Date (DD/MMM/YY)	Lot & batch number
6 weeks of age		____ / ____ / ____	
10 weeks of age		____ / ____ / ____	
14 weeks of age		____ / ____ / ____	

Routine immunization vaccines administered:

Clinic visit	Vaccines administered
At birth	
6 weeks of age	
10 weeks of age	
14 weeks of age	
18 weeks of age	
At any other age, specify age _____	

Signature of study investigator/s: _____

To be completed by the principal investigator

Is the event related to the study vaccine?

Unrelated Possibly related Probably related Definitely related

If unrelated to the vaccine, provide a reasonable explanation for the event (*e.g., other vaccine, blood collection, medical collection, etc.*) _____

_____Name and signature of PI: _____ Date / / /

Discontinuation Tracking Form – Vaccine Recipient

Date of the report (dd/mm/yy): / /

Date of study discontinuation (dd/mm/yy): / /

Note: This is the date the vaccine recipient is withdrawn from the study and may not be the same date as the report

Last clinic visit (circle one): 6 weeks / 10 weeks / 14 weeks

Date of last study clinic visit (dd/mm/yy): / /

Reasons (circle one of the choices listed below):

Discontinuation criteria as mentioned in study protocol:

1. Parent withdrew consent for participation (i.e., did not want child to participate any further).
2. The vaccine recipient received **polio vaccine** outside of the study. (**Complete protocol deviation form**)
3. Parent refused to allow collection of blood at 6 weeks of age. (**Complete protocol deviation form**)
4. Study staff were unable to collect blood at 6 weeks of age (**Complete protocol deviation form**)
5. Since enrolment, the vaccine recipient was diagnosed with a medical condition in which continued participation in the study posed a health risk (for example, immunodeficiency or bleeding disorder).
6. The vaccine recipient began taking immunosuppressive medications.

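### Discontinuation removes infant and sibling from all follow-up, not only from study doses, so later adverse events and informative nOPV2 stools are not collected

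*Protocol*

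**What the plan says.** Under Discontinuation Criteria (Vaccine Recipient), an infant given an outside polio vaccine leaves: "Vaccine recipients who received polio vaccines outside of the study, including any polio vaccine administered in polio campaigns, would be excluded from further study procedures". The list also contains "Identification of immunodeficiency disorder, bleeding disorder or another medical condition for which continued participation, in the opinion of the principal investigator, would pose a risk" and "Allergic reaction to a prior dose of polio vaccine, or its contents". Concomitant Medications and Vaccines adds "If the vaccine recipient needs to receive medications that cause immunosuppression, the vaccine recipient will be discontinued from the study". In Appendix A, the Discontinuation Tracking Form explains the discontinuation date thus: "This is the date the vaccine recipient is withdrawn from the study and may not be the same date as the report". No section provides for AE questioning, blood or stool after that date.

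Under Discontinuation Criteria (Sibling), the sibling stops whenever the infant is discontinued, and also after a polio dose of its own: "Siblings who receive polio vaccines during their participation in the study, including any polio vaccine administered in polio campaigns, would be excluded from further study".

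The analysis sections promise more than these rules deliver. Adverse Events (AEs) lists "Incidence rate of serious AEs during entire study period", and the same span for unsolicited events. Outcome variables counts household transmission as present when the sibling is nOPV2-positive at 1, 2 or 4 weeks after the infant's first vaccination. Primary Analytical Approach states "The primary analytical approach will be intention-to-treat", restricted to infants who have not withdrawn consent and have adequate enrolment and endpoint blood.

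The Adverse Event Form in Appendix A asks whether the event led to stopping the study or stopping later vaccinations. The criteria themselves offer no vaccination-only route.

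**The concern.** Stopping a study vaccine and stopping observation are separate decisions, and the protocol merges them. Two kinds of information are lost.

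**Safety.** An infant withdrawn for an allergic reaction, a newly found immunodeficiency or another medical condition has already been exposed to a live vaccine, which in Arms A and B is a new one. The plan offers no systematic way to learn of a new event in that infant after withdrawal. If rates were computed on time to discontinuation, the censoring would be tied to the child's medical course and could not be taken as uninformative.

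**Transmission.** Once an infant has received nOPV2, the household is exposed. The sibling's later stools remain evidence on transmission whatever then happens to the infant's participation.

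An analysis plan cannot recover specimens or reports that were never collected, so this has to be settled in the protocol.

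**Working it through.** **Inputs.** Follow-up runs from 6 to 18 weeks of age (Study Design). AEs are asked about at each clinic visit, at 10, 14 and 18 weeks (Recording, Monitoring and Reporting of Adverse Events). Stools are due at 7, 8 and 10 weeks in Arm A and at 8 and 10 weeks in Arms B and C (Table 1). The sample size is 238 per arm, 265 enrolled, for 90% power, a 10-point margin and 85% response.

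**1. The plan's own figures reproduce.**
- Non-inferiority formula, one-sided 0.05: n0 = 2 × 0.85 × 0.15 × (1.645 + 1.282)² / 0.10² ≈ 218.4.
- With continuity correction: n = (n0/4) × [1 + √(1 + 4/(n0 × 0.10))]² = 237.96, so 238.
- Attrition: 238 / 0.90 = 264.4, so 265.

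The point is therefore not a sample-size error. Loss of 265 − 238 = 27 per arm is already allowed for.

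**2. AE follow-up lost per discontinued infant (18 weeks minus age at discontinuation).**
- Just after the 6-week visit: 18 − 6 = 12 weeks, three clinic enquiries.
- Just after the 10-week visit: 18 − 10 = 8 weeks, two enquiries.
- Just after the 14-week visit: 18 − 14 = 4 weeks, one enquiry.

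**3. Stools lost per child of a discontinued pair (arms given nOPV2).**
- Before 7 weeks: 3 of 3 in Arm A, 2 of 2 in Arm B.
- Between 7 and 8 weeks: 2 of 3 in Arm A, 2 of 2 in Arm B.
- Between 8 and 10 weeks: 1 of 3 in Arm A, 1 of 2 in Arm B.
- After the 10-week stool: none.

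Transmission is scored as positive at any of the time points. If a pair with an incomplete series is counted, a missing stool can turn a positive into a non-positive but never the reverse. If the pair is dropped, its information is lost altogether. Detection is by type-specific PCR (Specimen Collection, Handling and Testing), so type 2 can still be read after bOPV, which carries types 1 and 3, or after inactivated vaccine.

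**4. How many children.** The documents give no rate for the rule-driven reasons. If total attrition matches the plan, the ceiling is 795 − 714 = 81 infants across all arms and all reasons. Some of these will be consent withdrawals, for whom nothing can be continued.

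**5. What the loss does not do.** At 85% response (one-sided 0.05, continuity-corrected), power is 0.900 with 238 analysed and 0.927 with all 265, so keeping every infant would gain at most 0.027. For 23% sibling shedding, the stated interval of 17.8–28.8% corresponds to about 240 siblings. Exact intervals are 17.9–29.0% at n = 238 and 18.1–28.6% at n = 265. Precision is hardly affected; the issue is which children and stools are missing.

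**The case against.** **The triggering event is recorded.** The Adverse Event Form has initial, follow-up and final reports and an outcome field, and time of resolution or stabilisation is required. Care for vaccine-related outcomes is free. This stands. The gap is limited to new events that begin after discontinuation, and it is not shown that reported incidence would be too low.

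**Exclusion after an outside dose has a reason.** The trial asks whether bOPV inhibits the response to nOPV2 (Justification for this Study). An Arm A infant given outside bOPV moves towards Arm B's exposure. The national schedule also includes fractional IPV at 6 and 14 weeks, and the risk section treats it as giving type 2 protection, so outside IPV can raise type 2 titres. Keeping such infants in the primary set would blur the contrast, which in a non-inferiority trial can favour the conclusion sought. This stands, and is why their endpoint blood should serve a sensitivity analysis only.

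**Sibling stools also serve the recombinant objective.** Recombination needs two strains in one cell, so outside OPV confounds the A versus B recombinant comparison and might alter acquisition of nOPV2. This stands for those stools. It gives no reason to stop sampling a sibling merely because the infant was, for example, started on immunosuppressive medication.

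**A stronger reading is tempting.** A reader might infer that the intention-to-treat comparison is biased by arm, because Arm A parents know that their infant gets no type 1 or 3 vaccine until 18 weeks and may seek bOPV elsewhere. The documents do not support this. They give no outside-vaccination rate by arm. All arms lack fractional IPV until 18 weeks, and Arm C lacks type 2 protection. Routine non-polio vaccines are given at study visits, and enrolment pauses around campaigns. Blood taken before discontinuation stays in the analysis. Any size is assumed: if a fraction L per arm is lost and response among the lost differs between arms by D, the difference shifts by about L × D. That is 0.02 × 10 = 0.2 points to 0.10 × 30 = 3.0 points against a margin of 10, with L and D both invented.

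**Conclusion.** The point holds as a gap in data collection and an inconsistency between sections. The criteria end all follow-up for reasons that call only for stopping study doses or for handling contaminated specimens in the analysis. The whole-study AE measures, the transmission definition and the Adverse Event Form all presuppose more.

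Each affected infant loses up to 12 weeks of AE follow-up. Each child of an affected pair loses up to three stools in Arm A or two in Arm B. The number affected is unknown, with a ceiling of 81 infants if attrition is as planned. Loss of sibling stools arises only from events between infant ages 6 and 10 weeks.

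The conclusion assumes that discontinuation means what the tracking form says, withdrawal from the study, and that no unstated follow-up takes place. It does not extend to infants without enrolment blood, who receive no study vaccine, or to withdrawn consent, a parental request to stop or early termination of the study. Differential loss by arm, its direction and any understatement of safety incidence are not established.

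**What to change.** Leave every criterion for stopping study vaccination as it is. Reconcile Discontinuation Criteria, Concomitant Medications and Vaccines, Adverse Events (AEs) and the Appendix A forms so that they separate stopping study vaccination from stopping follow-up. Then, unless the parent withdraws consent or refuses:

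- Continue AE questioning to 18 weeks of age, by phone if needed. Phone contact is already used after the first dose.
- Where the infant was discontinued after receiving nOPV2, collect the remaining scheduled infant and sibling stools.
- Flag stools taken after an outside polio dose in either child. Use them for type 2 shedding and transmission in a sensitivity analysis, and exclude them from the A versus B recombinant comparison when the outside dose was OPV.
- Endpoint blood after an outside polio dose may be drawn where the parent agrees and the draw is safe, for a sensitivity analysis only. Exclude these infants from per-protocol from the date of that dose.

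The cost is an amendment, a revised discontinuation form, a few calls and some visits that are already scheduled. The sample size does not change.
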